Figure 2 (from Martorell, Paulson et al., 2019): LFP and single unit response to audiovisual flicker in the hippocampus and prefrontal cortex in mice. A: Power spectral density (PSD) response to 40 Hz audio-visual flicker stimuli and no stimulation periods, with mean and standard deviation across recording days (left), power spectrum LFP response to audio-visual flicker stimulation of all recording days in CA1 (recording site with largest 40 Hz peak during 40 Hz audio-visual flicker per recording depth is shown) (right). B: In CA1, firing rate modulation of a single unit during 40 Hz audio-visual (AV) stimulation (left). Vector strength of responses to 40 Hz AV stimulation, random AV stimulation, and no stimulation periods (right, ****P<0.00005 40 Hz vs. no stim, 40 Hz vs. random; Kolmogorov-Smirnov test; 8 units and 3 units had VS values >0.25 for 40 Hz or random stim, respectively). In all statistical tests for panels B-C, results are significant after controlling for multiple comparisons using the Bonferroni correction unless otherwise stated. C: Same as in B for mPFC (right, ****P<0.00005 40 Hz vs. no stim, 40 Hz vs. random; Kolmogorov-Smirnov test; 5 units had 40 Hz stim VS values > 0.25). For B and C, vector strength is a measure of how much the firing of a given cell is phase-locked to the stimulus.

In this project, we aim to explore whether we can replicate these neural modulation and behavioral effects of flicker in humans. We ask 2 questions: 1) Can sensory flicker modulate the activity of the hippocampus, and potentially other high-order areas such as the prefrontal cortex, in humans? 2) Would such modulation be correlated with changes in cognition that are relevant to regions affected, such as memory in the case of the hippocampus? To explore these questions, we propose to study intracranial neural activity in treatment-resistant epileptic patients, at the level of populations of neurons (LFPs) and, when microelectrode recordings are present, at the level of individual neurons (single units), as a function of sensory flicker.

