1.3.1. Primary Outcome Measures

The primary outcome measure is the effect of sensory **flicker** exposure on local field potential (LFP): comparing mean power spectral density at the frequency of flicker being presented between flicker and baseline periods. [Time Frame: Up to 6 weeks]

Power spectral density of the LFP will be measured across stimulus frequencies and modalities of sensory flicker stimuli in visual areas, auditory areas, hippocampus and prefrontal cortex. The mean power spectral density measured in dB at the frequency of flicker being presented will be compared between flicker stimulation and no-stimulation baseline periods.

1.3.2 Secondary Outcome Measures:

The secondary outcome measure is the effect of sensory flicker on interictal epileptiform discharges (IEDs), which represent pathological activity often observed in epilepsy [Time Frame: Up to 6 weeks]

The effect of the sensory flicker will be evaluated by the comparison of the whole-brain rate of IEDs between sensory flicker stimulation and baseline (no stimulation).

1.3.3 Exploratory Outcome Measures:

- 1) To study whether sensory flicker exposure can entrain LFPs and modulate single neuron activity in higher cognitive areas such as the hippocampus and prefrontal cortex.
- 2) To identify the modality and frequency of flicker to which given brain regions are most efficiently modulated at the LFP and the single unit levels.
- 3) To identify potential effects of audiovisual flicker on various cognitive processes through a behavioral task.
 - a. If there are effects, to identify their electrophysiological correlates (such as changes in sharp-wave ripples' rate).
- 4) To compare the effects of sensory flicker modulation to direct electrical modulation of various neural circuits within individual subjects.

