2.2.3. Intracranial electroencephalographic (iEEG) activity

This study analyzes routine diagnostic EEG data that is generated using intracranial electrodes. The number, type, orientation, and size of the iEEG electrodes depend on the anatomy and clinical considerations per patient. Typically, there will be tens to hundreds of electrode contacts arranged as a depth, strip, and/or grid. An electrode may be relatively large (macroelectrode) or very small (microelectrode). Macroelectrode local field potentials (LFPs) consist of 0.1-1000 Hz signals obtained from iEEG contacts placed either within the brain (i.e. recorded from depth electrodes) or on the surface of the brain (i.e. recorded from subdural strip or grid electrodes). These signals will be acquired at 1000-2000 samples per second and 12-bit precision for electronic storage. Both the standard and investigational macroelectrode iEEGs are automatically stored to a 2-Petabyte RAID server that is securely managed by Emory Healthcare Information Services (EHc-IS). The stored data is directly accessed via a password-protected Epilepsy Monitoring Unit EMU data system that is securely managed by EHc-IS. Microelectrodes record signals at a sampling rate of up to 30,000 samples per second and 16-bit precision for electronic storage. These signals are then processed by applying a high-pass filter between 200 and 750 Hz, in order to extract the extracellular action potential waveforms (single unit activity) from neurons located in the vicinity of the recording contact.

2.2.4. Exposure to sensory pulses and flicker.

To expose the patient to sensory flicker and individual pulses sensory stimulation, we will use modified versions of the DAVID device (Mind Alive Inc., <https://mindalive.com/>), a commercially available device, and headphones or earbuds. Versions of the DAVID device were used in a recent study described above¹³ (Figure 4) and in many other human studies¹⁷⁻²⁴. Our device consists of opaque glasses containing LEDs to present light flashes, with or without see-through holes, as well as earbuds or headphones to present sound bursts. Patients will be exposed, for about 10

to 60 minutes at a time, to a sequence of sensory flicker trials each lasting a few seconds to 5 minutes, while their eyes are open or closed. Each trial may include the following modalities and frequencies of flicker:

- Modalities: auditory only, visual only, or audiovisual combined.

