- Frequencies: random, or anywhere from 3Hz to 200Hz.

Additionally, subjects may be exposed to individual pulses of light and/or sound, i.e. around or less than 1 pulse /second, for up to 20 minutes at a time.

For experiments characterizing neural response to sensory flicker, patients may be exposed for about 10 minutes to a single modality and frequency combination, such as 40Hz (gamma-like) audiovisual flicker, 5.5Hz (theta-like) audiovisual flicker, or random audiovisual flicker.

For one of the experiments testing the effects of sensory flicker on memory, patients may be exposed to audiovisual flicker for up to about 36 minutes at a time.

For another experiment, patients may be exposed to audiovisual flicker of a given frequency or random frequency, at modalities of visual only, auditory only, or audiovisual combined, for up to 1h at a time.

For another experiment testing the effects of sensory flicker on memory, patients may be exposed, eyes open, to visual flicker via a strip of LEDs secured to the perimeter of a monitor screen that presents images or words, or via wearing a customized DAVID device with glasses that have view holes; sound stimulus will be again provided via earbuds or headphones. In this experiment, sensory flicker would last for a few seconds at a time.

For other experiments testing the effects of sensory flicker on memory or interictal epileptiform discharges, patients may be exposed, eyes open, to visual and/or auditory flicker, anywhere from 10s to 60 minutes at a time, while performing on a spatial navigation task (see more details below). Visual flicker will be administered via customized DAVID device with glasses that have view holes, and auditory flicker will be administered via earbuds or headphones.

For most to all experiments involving exposure to visual and/or auditory stimuli, there will be an occluded condition. In this occluded condition, the subject will wear a sleeping mask or towel on their eyes (under the LED glasses mentioned above), and commercially available earplugs; in this condition, they will be exposed to similar visual and/or auditory stimuli as in the non-occluded condition. Subjects will be instructed on how to properly wear earplugs by specifying instructions similar to the ones available here: <https://www.cdc.gov/niosh/mining/content/earplug.html>.

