2.2.8. Memory consolidation experiment

To determine whether audiovisual flicker impacts memory consolidation, subjects may go through the following experimental paradigm or a similar one, based on Roberts et al.'s (2018)¹³ experiment (Figure 5).

Patients will view 4 series of words or images. In 2 of these series, they will be asked for each word or image whether it refers to a living thing, while in the other 2 series, they will be asked whether each word or image refers to something that is man-made. This will be followed by a 36-minutes period of exposure to audiovisual flicker (either random or 5.5Hz or 40Hz, via the customized DAVID device). Finally, they will undergo an unexpected test of memory for the words or images they've been exposed to (item recognition), as well as the associated contextual sorting they had to perform (alive vs man-made, i.e. source recognition).

For this experiment, depending on his or her choice, a patient may go through the task more than once on different days, being exposed to a different condition each time (random, 5.5Hz, or 40Hz audiovisual flicker). This would allow us to compare the effects of specific frequencies of audiovisual flicker on memory, in the same patients.

[figure not shown]

Figure 5: experimental paradigm from Roberts et al. (2018). In our experiment, we may use images instead of words, and patients will be tested for effects of either random, 5.5Hz or 40Hz audiovisual flicker on memory. In case a patient were to be tested for the effects of more than one type of sensory flicker, he or she would be tested for each type of sensory flicker on different days.

The anticipated duration of this experiment is about 120min for each day.

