5. STATISTICAL ANALYSIS

For objectives 1 and 2, we will perform analyses similar to the ones used in Martorell et al.'s study². We will perform a power spectral density analysis of LFP signal in function of frequency and modality (visual, auditory or audiovisual) of the sensory flicker stimulus, using multi-taper methods. Comparisons will be drawn between the mean power spectral density under a given condition and control (random sensory flicker or no flicker) condition, using the Wilcoxon rank-sum test with Bonferroni correction for multiple comparisons. To analyze firing rate modulation of single units to sensory flicker, we will produce a histogram of each single unit's firing rate

aligned to the onset of light and/or sound stimulus. Moreover, we will analyze how strongly the firing rate of single units is phase-locked to the stimulus being played, by calculating and comparing the vector strength of their firing rate modulation under different conditions, using the Kolmogorov-Smirnov test.

For objective 3, we will use similar methods as mentioned above, and compare the effect size of LFP entrainment and firing rate modulation in different brain regions, in function of various sensory flicker parameters (i.e. frequency and modality).

For objective 4, we will do within-subject comparison of the rate of interictal epileptiform discharges during various stimulation and/or baseline conditions. If normally distributed we will use t-test to compare the conditions, otherwise we will use repeated-measures ANOVA.

For objective 5, memory performance will be compared with a repeated-measures ANOVA across the different conditions (e.g. for example, 5.5Hz or 40Hz audiovisual flicker vs. random audiovisual flicker). For one of the memory experiments, performance in the case of random flicker will serve as the baseline from which we will infer any improvement or impairment in memory performance.

All neural data analyses will be performed in Python and/or MATLAB.

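### Exploratory single-unit phase locking: the Kolmogorov-Smirnov comparison of vector strength ignores within-unit pairing, and no spike-count rule is written (low priority, cheap to improve)

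*Combined protocol and SAP*

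**What the plan says.** Section 5 (Statistical Analysis) gives two single-unit items: a descriptive firing-rate histogram, and a comparison of phase locking, "comparing the vector strength of their firing rate modulation under different conditions, using the Kolmogorov-Smirnov test". No other test is named for phase locking. The section models its analyses on the cited mouse study. The Figure 2 legend in section 1.2.1 shows the same measure and test there: "Vector strength of responses to 40 Hz AV stimulation, random AV stimulation, and no stimulation periods". The legend also counts units above a fixed value: "8 units and 3 units had VS values >0.25 for 40 Hz or random stim, respectively".

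Neither document part mentions a within-unit test, a minimum spike count, matching of spikes, or a bias-corrected locking measure.

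On the design:
- Section 1.3.3 lists the outcome as exploratory: whether flicker "can entrain LFPs and modulate single neuron activity in higher cognitive areas".
- The data exist only in some patients (section 1.2.1: "when microelectrode recordings are present, at the level of individual neurons (single units").
- Section 2.2.4 describes "a sequence of sensory flicker trials each lasting a few seconds to 5 minutes", and says that for response-characterisation experiments "patients may be exposed for about 10 minutes to a single modality and frequency combination", with random flicker among the examples.
- Section 5 allows either random flicker or no flicker as the control for the LFP comparison. The length of a no-flicker period is not given.
- In the memory consolidation experiment (section 2.2.8), "a patient may go through the task more than once on different days, being exposed to a different condition each time".

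**The concern.** There are two separate weaknesses, and they act in opposite directions.

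**Pairing.** A unit held through flicker and control in one session is its own control. A two-sample Kolmogorov-Smirnov (KS) test treats the two sets of values as independent. If units differ stably in how strongly they lock, that spread hides a common shift.

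**Spike counts.** Vector strength cannot be negative, and a unit with no locking still has a positive expected value that grows as spikes become fewer. If one condition contributes fewer spikes per unit, it looks more locked for that reason alone. The comparison with no flicker is the exposed one.

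At stake is the only test named for single-unit phase locking. A real effect could be missed, or a difference in recording time could be read as a difference in locking.

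**Working it through.** The plan gives no number of units, firing rates, effect size or power for this analysis, so there is no figure to reproduce. The check is illustrative.

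**Inputs from the documents.** KS test on vector strength (section 5); about 10 minutes, or 600 s, per combination (section 2.2.4); the 0.25 value (Figure 2 legend).

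**Assumed inputs.** 30 or 50 units; log-normal firing rates with median 1 Hz and log-SD 0.8; Poisson counts floored at 10; von Mises phases; two-sided 5%. Control locking is either zero in every unit, or stable within a unit and varying between units as Beta(1,9), mean 0.10. Steps 1 to 3 have no patient effect.

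**Step 1: size of the bias.** With no locking and n spikes, the expected vector strength is about sqrt(π/(4n)) = 0.886/sqrt(n). For a 1 Hz unit:
- 600 s: 0.886/sqrt(600) = 0.036
- 300 s: 0.886/sqrt(300) = 0.051

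Halving the time therefore adds about 0.051 − 0.036 = 0.015, which is half of a true gain of 0.03. The chance that an unlocked unit exceeds 0.25 is about exp(−0.0625n): exp(−1.25) = 29% at 20 spikes, exp(−3.125) = 4% at 50, and exp(−6.25) = 0.2% at 100.

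**Step 2: power lost by ignoring pairing** (50 units, 600 s each, gain of 0.03 in every unit)

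| Control locking | KS | Count-matched signed-rank |
|---|---|---|
| Zero | 41% | 54% |
| Stable, varying between units | 20% | 97% |

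Repeat runs gave 40 to 42% v 54 to 57%, and 19 to 20% v 97 to 99%.

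**Step 3: KS false positives with no true difference** (30 units)

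| Time, flicker v control | No locking | Varying locking |
|---|---|---|
| 600 v 600 s | 2% | 0% |
| 600 v 480 s | 4% | 0.3% |
| 600 v 300 s | 29% | 0.4% |

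The large power loss and the large false-positive rate thus arise in different scenarios. Pairing without count matching makes matters worse: a signed-rank test on the raw values gives 61% false positives at 600 v 300 s with no locking. After count matching it gives 4.7 to 6.3%, if units are independent.

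**Step 4: units nested in patients.** Here there is no average effect, time is equal, locking is stable, there are 50 units, and a patient-level shift in vector strength has an assumed SD of 0.01 to 0.03.

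| Test | False positives |
|---|---|
| Unit-level signed-rank, 5 patients x 10 units | 12 to 32% |
| Unit-level signed-rank, 10 patients x 5 units | 5 to 16% |
| t-test on patient means | 4 to 7% |
| KS | 1% or less |

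**Step 5: price of patient-level inference.** With stable locking, a gain of 0.03 and shift SD 0.01, power is about 76 to 93% for patient means against 96 to 98% for the unit-level test. The lower figure goes with fewer patients.

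**The case against.** **What stands.**
- At equal time KS is conservative, and section 2.2.4 points to about 10 minutes each for flicker and random flicker, where the count bias is small.
- The large power loss needs stable differences in control locking, which the documents do not report. Without them the loss is modest.
- No passage says outright that each unit is held across the compared conditions. Where conditions fall on different days, as in section 2.2.8, pairing should not be assumed.
- KS looks at the whole distribution and a paired test at a shift, so the choice is partly one of question.
- The outcome is exploratory.

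**Stronger readings that the documents do not support.**
- A reader might infer that the planned test will point the wrong way. In the simulations that does happen with 600 s of flicker, 120 s of baseline and no control locking: for a true gain of 0.03, KS rejects in 98% of runs and the baseline has the higher mean in all of them. No section gives a 5:1 ratio, or any baseline length.
- A reader might infer that counts go unhandled. Section 5 refers to methods similar to the cited mouse study, which may contain a rule. What can be said is that none is written here.
- A reader might conclude that a unit-level signed-rank test should simply replace KS. Step 4 shows that this can exchange a conservative test for one that is too liberal for inference to patients.

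**Conclusion.** The point holds as a low-priority improvement to an exploratory analysis. For units recorded in both conditions, the named test gives up power: modestly if control locking is near zero (about 41% v 54%), heavily if units differ stably (about 20% v 97%). Separately, the unwritten spike-count rule leaves the no-flicker comparison open to bias. KS false positives are about 29% at 2:1 with no locking, near 0% if locking varies between units, and about 2% or less at equal time.

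Unequal counts are a possibility, not a finding. Every rate rests on the assumed units, firing rates, locking and patient effects. The absence of a written paired test and count rule, and the dependence of vector strength on spike count, do not rest on those assumptions. The primary LFP and secondary discharge-rate results are unaffected.

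**What to change.** Amend section 5 as follows.

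1. For units followed across conditions in the same session, equalise spike counts within unit, by matched durations or by random subsampling averaged over many draws. Set a minimum count in advance; the exceedance probabilities in step 1 are one way to choose it.
2. Take the within-unit difference in vector strength and base the main inference on patient-level summaries of it. A mixed model or a patient-level permutation that respects the nesting would also serve.
3. Report a unit-level signed-rank test only as descriptive or secondary, and never without count matching.
4. Keep KS, on count-matched data, as descriptive and for units not followed across conditions.
5. If the cited mouse analysis already handles counts, write its rule into section 5. The pairing point remains.

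The cost is a few lines of code and text, with no new data. Some spikes in the longer condition and some sparse units go unused. Power is lower than the unit-level test suggests. With few patients and control locking near zero, the patient-level test need not have more power than KS; what it gives there is an error rate that holds for patients.

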2.2.1. Electrode placement

Electrodes are implanted stereotactically to help localize the seizure focus. As a standard means to increase accuracy, the surgery is guided by contrasted MR images, with post-operative reimaging for confirmation. The electrodes (Adtech, PMT or DIXI) have contacts for electrophysiological (LFP) recording and for stimulation. An electrode may include macroelectrode contacts only or macro- and micro electrode contacts. All electrodes are FDA-approved equipment for recording intracranial EEG during presurgical evaluation. Number and

locations of electrodes will be placed on purely clinical grounds, but may be used thereafter for research purposes in consenting subjects under the supervision of the director of the epilepsy monitoring unit (a neurologist) and the supervising neurosurgeon.

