 - In their study, Wolf and Goosses⁴⁰ report 103 out of 1062 patients with epilepsy in their cohort to be photosensitive (i.e. having seizure or abnormal activity induced by photostimulation). Among patients with localization-related (focal) epilepsies in their cohort, only 2.7% showed photosensitivity. Based on this study and expert opinion, we expect that when photic stimulation triggers a seizure in epileptic patients, it typically occurs in patients that have a generalized type of epilepsy disorder. Most of our patients are highly selected to have focal epilepsy characterized by seizures starting in specific brain locations. Thus, we estimate that the risk of photic-induced seizures is very low in our patient population compared to the overall epilepsy patient population, except for: 1) rare patients whose epilepsies start in the occipital region or 2) rare cases where it is suspected that the patient may have a generalized type of epilepsy disorder. For such patients (1 and 2 above), we will first check that they have not been shown to be photosensitive; we will then coordinate with the clinical team to determine, on a patient-by-patient basis, whether exposure to visual flicker or individual light flashes is contraindicated with respect to clinical goals. Causing a photic-induced seizure in such patients, while not necessarily desirable for research, may provide additional information useful to the clinical team.
 - Most of our patients have already been tested for photosensitivity and photic-induced seizures during their phase I (scalp EEG) long term video seizure monitoring, at photic stimulation frequencies of 1-21Hz (for 10s trains). We will check each patient's health records to see whether they have been tested.

Patients that have been identified as photosensitive or susceptible to photic-induced seizures will not be enrolled in this study.

- Before running an experiment involving exposure to light flashes (individual flashes at around 1Hz or less, or higher frequency flicker), we will consult with the clinical team to confirm that the patient is not suspected to be sensitive to photic-induced seizures.

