A published human study¹³ involved audiovisual stimulation for 36 minutes at 5.5Hz, 14Hz, or exposure to white noise, using a device similar to one of the devices (customized DAVID devices) we will be using. Thus, we expect to find similar minimal levels of discomfort as were found in this study. At any point in the experiment, if any of the issues mentioned above manifest, or if the patient complains of discomfort, we will modify parameters of the light flicker or individual

light flashes (such as flicker frequencies tested, light intensity). If issues persist, we will discontinue exposure to light flashes for this subject.

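### Objective 3 compares regions and modalities scored in different, partly overlapping sets of patients, using independent-sample methods with no pairing or patient term

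*Combined protocol and SAP*

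**What the plan says.** Section 5 gives objective 3 one sentence. It begins "For objective 3, we will use similar methods as mentioned above" and goes on to say that the team will "compare the effect size of LFP entrainment and firing rate modulation in different brain regions", as a function of flicker frequency and modality. The methods above it are a comparison of mean power spectral density between a condition and its control, "using the Wilcoxon rank-sum test with Bonferroni correction for multiple comparisons", and for single units a comparison of vector strength "using the Kolmogorov-Smirnov test". No pairing, patient term, restriction to patients scored in both cells, or nesting of contacts within patient is stated. The next two objectives differ: for objective 4, "we will do within-subject comparison of the rate of interictal epileptiform discharges", and for objective 5 a repeated-measures ANOVA.

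Section 2.2.1 says that electrode number and "locations of electrodes will be placed on purely clinical grounds". Section 2.2.3 adds that coverage depends on each patient's anatomy and clinical needs, with from tens up to hundreds of contacts. Section 1.2.1 makes single-unit data conditional on microelectrodes being present.

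Exposure varies too. Section 2.2.4 allows a session with a single modality and frequency, and Section 4 expects most patients to join only one or a few experiments. If problems persist after parameters are modified, Section 3.2 states "we will discontinue exposure to light flashes for this subject"; Section 3.3 has a parallel rule for sound.

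By content, objective 3 corresponds to exploratory outcome 2 in Section 1.3.3. The objective numbers in Section 5 do not match the outcome list.

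**The concern.** Patients will differ in how strongly they respond to flicker. If region A is scored in one set of patients and region B in another that overlaps only in part, an unpaired comparison adds the difference between the two sets to the difference between the regions. Expressing each effect as flicker versus control can remove a patient's baseline power, but not that patient's responsiveness.

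Where the same patients supply both cells, as can happen for modalities and frequencies, the problem reverses. An independent-sample test leaves between-patient variance in the noise, becomes conservative and loses power.

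At stake is the reading of exploratory outcome 2: which modality and frequency work best in a given region, and any ranking of regions built on it.

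**Working it through.** **What can be reproduced.** Nothing numerical. Section 5 gives no alpha, variance, effect size or sample-size derivation for objective 3, and the roughly 100 patients in Section 4 are a recruitment aim across all experiments. The documents give no coverage by region and no overlap. Everything below therefore rests on assumed inputs and shows direction and possible size only.

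**Check 1: regions, one score per patient and region.** Assumptions: 20 patients with visual contacts, 60 with hippocampal contacts, 12 with both (20 + 60 - 12 = 68 patients); between-patient variance 0.5 and residual variance 0.5, so total SD 1; no true region difference; two-sided 0.05. Patients with visual contacts are assumed to differ in overall responsiveness by D. The expected spurious region difference is D minus the part of D carried by the 12 overlapping patients in the hippocampal mean:

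D x (1 - 12/60) = 0.8 D

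This is 0.40 SD at D = 0.5 and 0.64 SD at D = 0.8. Simulated false-positive rates:

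| D (SD) | Unpaired rank-sum |
|---|---|
| 0 | about 3% |
| 0.1 | about 4% |
| 0.2 | about 7% |
| 0.3 | about 12% |
| 0.5 | about 29% |
| 0.8 | about 68% |

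The signed-rank test in the 12 patients with both regions stayed at about 4-5% throughout, because the patient effect cancels in each difference. Repeat runs moved the unpaired rates by one to three percentage points.

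**Check 2: regions, contacts pooled.** Assumptions: 100 patients, 10 contacts per region per patient, total variance 1, no true region difference and D = 0. The pooled rank-sum test then treats contacts from one patient as independent. False-positive rates by within-patient correlation:

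| Patients with both regions | 0.1 | 0.3 | 0.5 |
|---|---|---|---|
| none | 15% | 28% | 40% |
| half | 8% | 14% | 18% |
| all | 4% | 2.5% | 0.6% |

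The error rate is thus wrong even without a responsiveness difference: too high when overlap is low, too low when it is complete. If patients with region A only respond D higher and a share v has both regions, the rest being split equally, the spurious difference is D(1 - v)/(1 + v). At D = 0.5 this is 0.50, 0.30, 0.17 and 0.07 SD for v = 0, 0.25, 0.50 and 0.75. It vanishes at full overlap.

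**Check 3: two modalities in the same patients.** Assumptions: 40 patients supply both, with the same variance split. The unpaired test has about 1% type I error. For a true 0.5 SD difference it has about 61% power, against 87% for the paired test.

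**Cost of restricting to the overlap.** Under the inputs of Check 1 with D = 0 and a true region difference of 0.8 SD, power is about 66% for the 12-patient paired test and 85% for the unpaired test.

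**The case against.** The strongest reply is that this is exploratory. That stands: the primary outcome compares flicker with baseline inside a region, the secondary outcome is the discharge rate, and neither depends on this contrast. A reader might infer that the central question, whether flicker reaches hippocampus and prefrontal cortex, is compromised. It is not, because flicker versus control within those regions answers it.

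Second, the test is not fully specified. The rank-sum test is named for condition versus control, and similar methods need not mean that exact test between regions. This is fair. The defect is that objective 3 inherits independent-sample methods and nothing in the text adds a patient term, while objectives 4 and 5 have within-patient wording.

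Third, the larger shifts are assumptions. Nothing in the documents shows that visually covered patients respond differently. At 0.1 SD the unpaired test gives about 4%, and with many contacts per patient the overlap could be large.

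Two further inferences are tempting. One is that many patients will lack visual-area data and that those who have it are mostly occipital-onset cases. Section 3.2 does speak of "rare patients whose epilepsies start in the occipital region", but that describes where seizures start, not where contacts lie; contacts can lie outside the onset zone. The other is that patients who lose light exposure contribute auditory data only. The withdrawal rule is conditional and carries no expected number, sound can be withdrawn too, and nothing says that light data already collected are discarded. A session may also mix modalities, so the modality part is secondary.

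**Conclusion.** The concern holds for the exploratory comparison of regions, modalities and frequencies, and only there. Followed as written, Section 5 can mix region with patient and gives incorrect error rates, so this is more than missing detail. The size for this trial cannot be computed. Under the assumed coverage of 20, 60 and 12 patients, with half the variance between patients, the unpaired false-positive rate is close to nominal for shifts up to about 0.2 SD, about 12% at 0.3, 29% at 0.5 and 68% at 0.8. The bias shrinks as overlap grows. For modality and frequency contrasts in the same patients, the loss is power rather than validity. The documents do not support extending the point to the primary or secondary outcome, or asserting a particular link between visual coverage and occipital epilepsy.

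**What to change.** Amend Section 5, objective 3, as follows.

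- **Modality and frequency contrasts:** make them within patient. Average contacts per patient and cell, and apply a signed-rank test to the paired differences.
- **Region contrasts:** use the within-patient comparison in patients scored in both regions as the unconfounded estimate. Accompany it with a mixed model that has a patient random effect, with contacts and single units nested in patient, so that single-region patients are kept. The paired estimate remains the reference because the mixed model also draws on between-patient information.
- **Reporting:** for each region-by-modality cell, give the numbers of patients and of contacts or units, the overlap with the cell it is compared with, and the reasons for missing cells.

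The cost is analysis wording and one coverage table, with no new data and no change to any clinical rule. The overlap-only region contrast uses fewer patients and has less power (about 66% against 85% in the example above), and with very few overlapping patients it may be uninformative. That is a reason to report the overlap and to allow the mixed model. Pairing the modality and frequency contrasts costs no power where the same patients supply both cells.
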